## **13.0 CRITERIA FOR REMOVAL FROM STUDY**

Consent for participation in the study may be withdrawn by the patient or patient's health care proxy at any time.

If at any time, the patient develops clinically significant progressive disease, s/he will be withdrawn from the study and referred for alternative therapy.

If at any time the patient is found to be ineligible for the protocol as designated in the section on Criteria for Subject Eligibility (i.e., a change in diagnosis), the patient will be removed from the study.

If at any time, the protocol therapy jeopardizes the safety of the patient, s/he may be withdrawn from the study.

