5. To assess the time to response onset in following Talimogene Laherparepvec with or without radiotherapy. It is expected that the time to response onset in patients randomized to receive Talimogene Laherparepvec will be similar to previous studies of Talimogene Laherparepvec alone (median 4.1 months, range 1.2-16.9 months). It is anticipated that the time to response onset in patients receiving Talimogene Laherparepvec and radiotherapy will be earlier than prior studies of Talimogene Laherparepvec alone.

6. To estimate progression free and overall survival in patients receiving Talimogene Laherparepvec with or without radiotherapy for cutaneous metastases from melanoma and Merkel cell carcinoma. Progression free survival will be defined as the time elapsed from start of protocol treatment until progression (according to mWHO criteria) or death.

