## 10.0 EVALUATION DURING TREATMENT/INTERVENTION

Study Timeline	Pre-Treatment	Treatment									End of Treatment 	Follow-Up 
		0 (1)	3 (1)	5 (1)	7 (1) 	9 (1)	11 (1)	13 (1)	15 (1)	16 (1)		
Week (+/-)	-4 to 0											
Assessments												
Pathology Review	X											
PET/CT (with or without contrast)	X									X		
Quality of life questionnaires	X									X		
Digital photography	X									X		
Adverse event		X	X	X	X	X	X	X	X	X		X

review 											
ECOG performance status	X	X	X	X	X		X		X	X	
Vital signs (weight, heart rate, blood pressure, respiratory rate, oxygen saturation)	X	X	X	X	X		X		X	X	
Physical exam	X	X	X	X	X		X		X	X	
Complete medical history	X										
Hepatitis B Surface Antigen, Hepatitis B Core Antibody (total), hepatitis B surface Antibody, Hepatitis C Antibody 	X										
Comprehensive metabolic profile	X									X	
Basic metabolic profile		X	X	X	X		X		X		
Complete blood count	X	X	X	X	X		X		X		
PT&APTT	X	X	X	X	X		X		X		
Pregnancy testing (blood or urine); WOCBP only	X 		X		X		X		X		
Research blood test 		X	X	X	X		X		X		
Research skin punch biopsy 		X			X				X		
Treatment											
TALIMOGENE LAHERPAREPVEC		X	X	X	X	X	X	X	X†		
Radiation therapy			X*								

†Patients with potential for clinical benefit may continue TALIMOGENE LAHERPAREPVEC after week 15 every 2 weeks for up to 24 weeks (as determined by treating clinician)

\*Only for Arm A; first fraction given 6 (+/- 2) hours after week 3 TALIMOGENE LAHERPAREPVEC administration; 2nd and 3rd fraction given every 3-6 days over no more than 14 days

Including Appendix C, "NCI PRO-CTCAE v1.0"

Within 2 weeks of starting Talimogene Laherparepvec treatment

 Research bloods will be 3 tubes (3 CPT) at each time point; stored at immune monitoring core facility for up to 1 year after completion of study

One lavender top (EDTA) tube of blood will be drawn on the same day as the research skin punch biopsy; window for biopsy will be +/- 3 weeks

Additional testing to evaluate for hepatitis maybe required depending on the serological results

For patients that discontinue TVEC before week 16, the End of Treatment visit occurs after last dose of TVEC

Follow-Up at week 20 or 4 weeks after last TVEC dose

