### **11.1.4**

#### **Talimogene Laherparepvec Dosage Adjustments, Delays, Rules for Withholding or Restarting, Permanent Discontinuation**

If talimogene laherparepvec treatment was delayed by > 2 weeks, that dose will be deemed to have been missed and the subject will proceed to the next scheduled treatment visit. Dose reductions of talimogene laherparepvec is not permitted, other than a reduction in the volume injected due to a disease response.

If a subject experiences any of the following treatment-related toxicities, talimogene laherparepvec administration should be delayed until the toxicity has resolved to at least CTCAR grade 1 or baseline:

- Grade 2 or greater immune-mediated adverse events, with the exception of vitiligo
- Grade 2 or greater allergic reactions
- Any other grade 3 or greater hematologic or non-hematologic toxicity

Subjects who are receiving talimogene laherparepvec may not receive systemic antiherpetic drugs (eg, acyclovir, valacyclovir, famciclovir), but may receive a topically administered antiherpetic drug more than 20 cm from a talimogene laherparepvec injection site. Dosing should be permanently discontinued if, in the opinion of the investigator, the subject develops clinical evidence of any systemic herpes infection (such as encephalitis or disseminated infection). If the subject requires corticosteroid dosing of > 10 mg prednisone daily (or equivalent) for related toxicities, talimogene laherparepvec dosing must be withheld until the corticosteroid dose has decreased to  $\leq$  10 mg prednisone daily (or equivalent).

Talimogene laherparepvec treatment should be continued based on the potential benefit/risk assessment of the subject. If talimogene laherparepvec dosing is delayed by more than 4 weeks from the date of the planned dose (ie, approximately 6 weeks or 7 weeks depending whether the patient is receiving Q2W or Q3W dosing from the previous dose) due to the occurrence of an adverse event that is considered related to talimogene laherparepvec, the subject must be permanently withdrawn from talimogene laherparepvec treatment.

Talimogene laherparepvec is to be permanently discontinued for subjects meeting any of the following criteria:

- The subject, for any reason, requires treatment with another anticancer therapeutic agent for treatment of the study disease. In this case, discontinuation from the treatment occurs immediately upon introduction of the new agent.
- Confirmed PD

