Note that in the above, all patients are assumed evaluable. However, it might happen that some patients are not evaluable due to various reasons such as withdrawal or loss to follow-up, etc. Such inevaluable patients will be replaced. We expect that about 13% of patients might need to be replaced. In other words, we expect to enroll up to 34 patients in total. The clinical efficacy of Talimogene Laherparepvec will be measured by the ORR and summarized by the sample proportion for each of the two arms. A comparison will be done between the two arms. Safety of Talimogene Laherparepvec will be summarized and compared similarly. QOL total and subscale scores will be summarized numerically and graphically, and trends will be observed and reported per arm. Wilcoxon rank sum tests will also be used to compare the QOL scores between the two arms for each assessment time point. DOR will be assessed using actuarial curves based on patients who achieved response and compared between the two arms using a stratified log-rank test. Time to response onset, progression free and overall survival will be analyzed in a similar way but will be based on all patients. Immunologic response data will be summarized descriptively, with mean, median and standard deviations calculated.

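### Section 13 ends study participation at progression and no section collects survival status afterwards, so overall survival cannot be validly estimated as the plan stands

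*Combined protocol and SAP*

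**What the plan says.** Section 13.0 has three relevant removal rules, all from the study and not only from treatment:

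- Progression, mandatory: "If at any time, the patient develops clinically significant progressive disease, s/he will be withdrawn from the study and referred for alternative therapy".
- Ineligibility found later, mandatory: "the patient will be removed from the study".
- Safety, discretionary: "If at any time, the protocol therapy jeopardizes the safety of the patient, s/he may be withdrawn from the study".

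Section 11.1.4 keeps a separate list, which concerns the drug only: "Talimogene laherparepvec is to be permanently discontinued for subjects meeting any of the following criteria". The list includes confirmed PD, toxicity requiring a long dose delay, and the need for another anticancer agent, where "discontinuation from the treatment occurs immediately upon introduction of the new agent". It does not mention leaving the study.

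Secondary Objective 6 in Section 2.0 is "To estimate progression free and overall survival in patients receiving Talimogene Laherparepvec with or without radiotherapy". It defines progression-free survival but not overall survival. Section 14.0 adds: "Time to response onset, progression free and overall survival will be analyzed in a similar way but will be based on all patients". In context, that means actuarial curves and a stratified log-rank test.

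The last visit in the Section 10.0 schedule is "Follow-Up at week 20 or 4 weeks after last TVEC dose". Its only item is an adverse-event review. No section schedules a survival contact.

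**The concern.** In advanced cancer, death usually follows progression. If observation stops at progression, patients leave the risk set just as their hazard of death rises. This censoring is informative: the Kaplan-Meier curve then estimates survival as if only death without prior progression could occur. The log-rank test has the same problem, and if radiotherapy changes the time to progression, the arms are also censored differently.

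The schedule adds a second limit. A patient who never progresses also has no planned contact after the final adverse-event review, so information on survival ends early for everyone.

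There is also a wording conflict on safety. Progression or toxicity stops the drug under Section 11.1.4 but can end study participation under Section 13. The protocol does not say whether the visits and reporting due after the last dose still apply to a withdrawn patient.

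**Working it through.** **The plan's own figures.** The documents give no survival rate, death count or survival follow-up time, so there is no stated figure to reproduce. The two-stage design in Section 14.0 does reproduce and is not touched by this point: early stopping is 0.925^9 = 0.496 (stated 0.50) and 0.73^9 = 0.059 (stated 0.06), with type I error 0.094 and power 0.802. Enrolment is 30 × 1.13 = 33.9, hence 34.

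**All rates below are assumptions.** Both models treat every progression as leading to withdrawal. If some progressions are not judged clinically significant, more deaths would be seen.

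**1. Bias from stopping at progression.** Let λ = ln 2 / (median time to progression or death), h0 = monthly death hazard before progression, h1 = monthly death hazard after it.

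- True survival: S(T) = e^(−λT) + (λ − h0)(e^(−h1·T) − e^(−λT))/(λ − h1).
- Estimate when censored at progression: e^(−h0·T).
- Deaths counted: (h0/λ)(1 − e^(−λT)).

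Example with median 6 months, h0 = 0.01, h1 = 0.04, T = 12: λ = 0.1155, so S = 0.25 + 0.1055 × (0.619 − 0.25)/0.0755 = 0.765. The censored estimate is e^(−0.12) = 0.887. Deaths counted are 0.0866 × 0.75 = 0.065 of patients, against 0.235 in truth, so 72% are missed.

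Over all eight combinations (median 3 or 6 months; h0 0.005 or 0.01; h1 0.04 or 0.08):

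| Time | True survival | Estimate censored at progression | Deaths after progression, as a share of all deaths |
|---|---|---|---|
| 12 months | 53–79% | 89–94% | 72–96% |
| Week 20 (4.6 months) | 85–95% | 95.5–98% | 50–90% |

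For 30 evaluable patients at 12 months, 30 × 0.020 to 30 × 0.065 gives 0.6 to 1.9 deaths counted. The true number is 30 × 0.21 to 30 × 0.47, or about 6 to 14.

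**2. Separating Section 13 from the schedule.** Let f be the share of first events that are deaths, m1 the median time to progression or death and m2 the median survival after progression, with λ = ln 2/m1 and h = ln 2/m2.

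- All deaths by T: D(T) = 1 − e^(−λT) − (1 − f)λ(e^(−hT) − e^(−λT))/(λ − h).
- Counted under Section 13 alone: f(1 − e^(−λT)).
- Counted under the week-20 limit alone: D(4.6).
- Counted under both: f(1 − e^(−4.6λ)).

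Example with m1 = 6, m2 = 12, f = 20%, T = 12: D = 1 − 0.25 − 0.8 × 2 × (0.5 − 0.25) = 0.35. Section 13 alone counts 0.2 × 0.75 = 0.15, or 43%. Week 20 alone counts 0.126, or 36%. Both count 0.2 × 0.412 = 0.082, or 24%.

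| m1, m2 (months), f | Section 13 alone | Week 20 alone | Both |
|---|---|---|---|
| 3, 9, 5% | 10% | 32% | 7% |
| 3, 18, 5% | 16% | 32% | 11% |
| 6, 12, 10% | 25% | 30% | 14% |
| 6, 18, 10% | 32% | 32% | 17% |
| 6, 12, 20% | 43% | 36% | 24% |
| 8, 24, 10% | 38% | 31% | 19% |

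These are percentages of deaths in the first 12 months. For the first 24 months the ranges are 6–29%, 14–20% and 4–13%.

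**3. Longer treatment.** If the optional extension of up to 24 weeks runs from week 15, the last review falls at 15 + 24 + 4 = week 43 (9.9 months). With exponential survival and an assumed median of 6 to 36 months, 84–91% of 12-month deaths and 47–73% of 24-month deaths occur by then. The schedule limit is milder for those patients but does not disappear.

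**4. Safety provisions beside Section 13.** Each is tied to the last dose or treatment, and none exempts a withdrawn patient:

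- Section 9.0 and Section 10.0 footnote 6: End of Treatment visit, with adverse-event review, when the drug stops early.
- Sections 9.0 and 10.0: adverse-event review at 4 weeks (28 days).
- Section 2.0, Secondary Objective 2: adverse-event window to 5 weeks (35 days).
- Section 11.1.3.1: dose-limiting toxicities to 30 days.
- Section 17.2: serious events to 30 days, and later ones if possibly related.

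**The case against.** Four counter-arguments deserve weight.

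- **Safety.** A reader might infer from Section 13 that the patients at highest risk lose adverse-event follow-up. The documents do not support that. Collection is tied to the last dose, serious-event reporting is mandatory, and withdrawal for safety is optional. What remains is that no section says these duties continue after a Section 13 withdrawal. In a single-site trial, the risk is inconsistent handling by staff, not a difference between sites.
- **Cause.** A reader might charge the whole 12-month bias to Section 13. That is also too strong. The 12-month comparison assumes complete follow-up, which the protocol schedules for nobody. The week-20 limit alone would lose most 12-month deaths in the six scenarios, so rewording Section 13 without adding survival follow-up would not repair the endpoint.
- **Other endpoints.** Section 12.0 keeps patients who leave for symptomatic progression, death or toxicity evaluable, so the primary endpoint is largely protected. Withdrawal at progression does not remove a progression-free survival event, because the event has already occurred.
- **Importance.** Overall survival is one of several secondary endpoints in a small phase II trial, and no go/no-go rule uses it. This limits the severity.

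None of this supplies survival data after withdrawal. The staff could look up deaths in the medical record, but the plan does not require it, and Section 13 points the other way.

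**Conclusion.** The point holds for overall survival. A stated rule ends observation at progression, no section restores it, and the schedule stops early for everyone else. The curve and the between-arm test would then mainly reflect death without prior progression.

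The direction is the same in every scenario tried: stopping at progression alone misses 57–90% of 12-month deaths in the six-scenario set and 72–96% in the eight-scenario set. The exact size is not a documented quantity. It rests on assumed exponential rates and on withdrawal at every progression.

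For safety, the finding is limited to an unreconciled conflict between Section 13 and the follow-up rules; no loss is shown. The primary endpoint and the sample size are not in question. This should be fixed, but it does not undermine the trial's main decision.

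**What to change.** 1. In Section 13.0, separate discontinuation of protocol treatment from withdrawal from the study. State that the adverse-event review after treatment, serious-event reporting and vital-status follow-up still apply when treatment stops for progression, safety or later-found ineligibility, unless the patient withdraws consent for follow-up.
2. In Sections 2.0 and 14.0, define overall survival: start date, death from any cause, and censoring at the date last known alive.
3. In Sections 9.0 and 10.0, add record-based vital-status collection for all randomised patients to a stated study cut-off. Capture of deaths should then be complete to that date, apart from patients lost to follow-up or withdrawing consent.
4. If vital status will not be collected, state that overall survival cannot be validly estimated and drop it as an endpoint.
5. The sponsor should reconcile the different progression wording in Sections 13.0 and 11.1.4, and the 4-week, 5-week and 30-day safety windows. Which clinical rule applies is for the sponsor to decide.

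The cost is a wording amendment and longer record follow-up of at most 34 patients at one centre. The sample size and the two-stage decision rule do not change.

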## **14.0 BIOSTATISTICS**

Patients will be randomized into two separate arms (stratified by disease type), each of which will use a Simon's optimal two-stage design to assess the primary endpoint of systemic response (defined as patients achieving partial response or complete response) of a metastasis that was not injected or irradiated. The single largest measurable metastatic disease site will be used for this assessment 16 weeks after the first dose of Talimogene Laherparepvec. For each arm, a 7.5% or lower response rate is considered not promising, a 27% or higher response rate is considered promising, and the probabilities of a type I error (falsely accepting a non-promising therapy) and type II error (falsely rejecting a promising therapy) are set to 0.10 and 0.20, respectively.

In the first stage, 9 evaluable patients will be accrued to each arm. If at least 1 patient achieves response among these 9 patients, then an additional 6 patients will be accrued to that arm in the second stage. If no patients achieve response then that arm will be closed to further accrual and declared negative. At the end of the trial if 3 or more patients achieve response out of 15 then that treatment arm will be considered worthy of further investigation. This design has an early stopping probability of 0.06 if the true response rate is at least 27% and 0.50 if the true response rate is at most 7.5%. Although a comparison will be done between the two arms by a two-sample proportion test on response rates, this sample size may not have enough power to distinguish the two arms. Thus if both treatment arms are declared worthy of further investigation compared to historical control rate, the treatment arm with the higher observed response rate will be selected as the preferred treatment modality for future studies. The probabilities of selecting correctly the arm with the true higher response rate are given below. The maximum number of patients needed is 30, for which we expect to enroll in 36 months.

True response rates for the two arms	27% vs 35%	27% vs 40%	27% vs 45%	30% vs 35%	30% vs 40%	35% vs 40%	35% vs 45%	35% vs 50%
Probability of picking the correct arm (i.e., the one with the higher response rate)	0.61	0.72	0.80	0.54	0.65	0.54	0.65	0.74

Note that in the above, all patients are assumed evaluable. However, it might happen that some patients are not evaluable due to various reasons such as withdrawal or loss to follow-up, etc. Such inevaluable patients will be replaced. We expect that about 13% of patients might need to be replaced. In other words, we expect to enroll up to 34 patients in total. The clinical efficacy of Talimogene Laherparepvec will be measured by the ORR and summarized by the sample proportion for each of the two arms. A comparison will be done between the two arms. Safety of Talimogene Laherparepvec will be summarized and compared similarly. QOL total and subscale scores will be summarized numerically and graphically, and trends will be observed and reported per arm. Wilcoxon rank sum tests will also be used to compare the QOL scores between the two arms for each assessment time point. DOR will be assessed using actuarial curves based on patients who achieved response and compared between the two arms using a stratified log-rank test. Time to response onset, progression free and overall survival will be analyzed in a similar way but will be based on all patients. Immunologic response data will be summarized descriptively, with mean, median and standard deviations calculated.

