### **15.2 Randomization**

Patients will be randomized into two separate arms (stratified by disease type). Once the participant's eligibility is established, the registration will be finalized and the participants will be randomized using the Clinical Research Database (CRDB). Randomization will be accomplished by the method of random permuted block, and will be stratified by disease type. After treatment arm is determined by randomization, RSAs at MSKCC will notify the physicians at MSKCC of the treatment arm and participant ID via email within 24 hours of randomization.

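### Randomisation and the log-rank tests are stratified by disease type, but the between-arm test of systemic response is not; it is valid, and loses power only if response differs strongly by tumour type

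*Combined protocol and SAP*

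**What the plan says.** Section 15.2 (Randomization) states: "Randomization will be accomplished by the method of random permuted block, and will be stratified by disease type". Section 14.0 (Biostatistics) repeats the stratification. The levels of disease type are not listed; the eligibility criteria in section 6.1 name melanoma, Merkel cell carcinoma and other solid tumours.

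Section 14.0 then handles the between-arm comparisons in three ways:

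- Systemic response: "a comparison will be done between the two arms by a two-sample proportion test on response rates". No stratified or adjusted version appears anywhere, and neither the significance level nor the sidedness is given.
- Duration of response: "compared between the two arms using a stratified log-rank test". Time to response, PFS and OS are to follow the same approach.
- ORR and safety: a comparison is promised, but no test is named.

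The plan is frank about the response comparison: "this sample size may not have enough power to distinguish the two arms". If both arms pass their own two-stage rule, "the treatment arm with the higher observed response rate will be selected as the preferred treatment modality for future studies".

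**The concern.** The same section stratifies its time-to-event comparisons by the randomisation factor but not the comparison on its primary endpoint, and gives no reason for the difference. If response depends on tumour type, stratified randomisation balances the arms on a prognostic factor, while the unstratified test still counts the variation between tumour types as error. Its standard error is then too large, its true size drops below nominal, and power is lost. What is at stake is the efficiency of a comparison that already has little power.

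**Working it through.** **Inputs from the documents (section 14.0).** Up to 15 evaluable patients per arm; stage 1 of 9; go on with at least 1 response; success with at least 3 of 15; "a 7.5% or lower response rate is considered not promising, a 27% or higher response rate is considered promising".

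**Assumptions.** Two-sided 0.05; three strata; stratum sizes and stratum response rates as shown; equal stratum sizes in the two arms; both arms reach 15. The documents supply none of these.

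**1. The plan's own figures.** Early stopping probability is (1 − p)^9: 0.73^9 = 0.059 and 0.925^9 = 0.496, matching the stated 0.06 and 0.50. The probability of success is the sum over x = 1 to 9 of P(X1 = x)·P(X2 ≥ 3 − x), with X1 ~ Bin(9, p) and X2 ~ Bin(6, p). This gives 0.094 at 7.5% (limit 0.10) and 0.802 at 27% (required 0.80). Choosing the better arm when it passes and the other arm either fails or has fewer responses gives 0.608, 0.715, 0.803, 0.538, 0.651, 0.539, 0.648 and 0.745, which match the selection table. None of these figures uses the two-sample test.

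**2. Power of the planned test.** The plan states none. By the normal approximation at 15 per arm it is about 0.07 (27% vs 35%), 0.11 (27% vs 40%), 0.17 (27% vs 45%) and 0.13 (35% vs 50%).

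**3. Why ignoring the strata is conservative.** The pooled test uses variance p̄(1 − p̄), while the true variance under stratified allocation is the average of p_h(1 − p_h). With 50/20/2% and 7/4/4:
- p̄ = (7×0.50 + 4×0.20 + 4×0.02)/15 = 0.292, so p̄(1 − p̄) = 0.2067.
- Average within-stratum variance = (7×0.25 + 4×0.16 + 4×0.0196)/15 = 0.1646.
- Ratio = 0.796, so the pooled z has standard deviation √0.796 = 0.892.
- Large-sample size = 2[1 − Φ(1.96/0.892)] = 0.028 instead of 0.05.

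**4. Size and power at 15 per arm, split 7/4/4.** The pooled z-test is compared with Cochran-Mantel-Haenszel (CMH) and with the exact conditional stratified test. CMH is Σ(a_h − n_Ah·m_h/T_h) divided by the square root of Σ n_Ah·n_Bh·m_h(T_h − m_h)/[T_h²(T_h − 1)], without continuity correction. Here a_h is the number of responders in one arm, m_h the responders and T_h the patients in stratum h. All (8×5×5)² = 40,000 possible outcomes were enumerated with their binomial probabilities.

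| Assumed stratum rates | Pooled z | CMH | Exact stratified |
|---|---|---|---|
| 50/20/2% in both arms (size) | 0.033 | 0.047 | 0.015 |
| 50/20/2% vs 90/60/20% | 0.44 | 0.60 | 0.45 |
| 30/10/2% vs 80/50/10% | 0.57 | 0.66 | 0.50 |
| 40/20/10% vs 60/35/20% | 0.14 | 0.16 | 0.08 |
| 12/5/2% vs 40/20/10% | 0.27 | 0.27 | 0.14 |
| 7.5% vs 27% in all strata | 0.28 | 0.28 | 0.15 |
| 27% vs 45% in all strata | 0.18 | 0.16 | 0.09 |

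**5. Other splits and a common odds ratio (OR).** Simulation with 400,000 trials per scenario, splits 8/4/3 and 5/5/5, pooled z vs CMH:
- Equal rates (27%): size 0.054 vs 0.046–0.047; power at OR 2.2 is 0.175 vs 0.162.
- Moderate differences (15/27/40%): size 0.047–0.049 vs 0.047–0.048; power 0.150–0.153 vs 0.147–0.157 at OR 2.2, and 0.49 vs 0.50–0.52 at OR 5.
- Strong differences (5/25/55%): size 0.026–0.032 vs 0.043–0.047; power 0.08–0.09 vs 0.12–0.14 at OR 2.2, and 0.28–0.30 vs 0.38–0.43 at OR 5.

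**The case against.** The strongest defence is that no decision rests on this test. Each arm is judged by its own Simon rule, the preferred arm is chosen by the higher observed rate, and the plan itself concedes that power is low. That stands, and it limits the weight of the point.

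Second, the large gains come from extreme scenarios. In the two with a clear benefit the overall rates are about 29% vs 63% and 17% vs 53%, and both upper values exceed the highest rate in the plan's selection table (50%). With moderate differences the gain is only about 1 to 2 points, and with none the unstratified test is not conservative at all. That also stands: the benefit depends on strong differences between tumour types, and the documents give no rates by type.

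Third, with about 30 patients one might prefer an exact stratified test. The table shows that this would defeat the purpose: its size is 0.015 against 0.033 for the planned test, and its power is lower in every scenario except the most extreme, where the two are level.

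None of this explains why one section stratifies some comparisons and not others. Stratifying costs up to about 1 point when tumour types do not differ, and recovers 9 to 16 points in the two scenarios with the strongest differences.

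**Conclusion.** The mismatch is in the text and worth correcting, as a modest improvement to a supporting comparison. If response differs strongly by tumour type, the planned test has a true size of about 0.03 and gives up power: 0.44 against 0.60, and 0.57 against 0.66, in the 7/4/4 scenarios. Under moderate differences the loss is about 1 to 2 points at most. All these figures rest on assumed stratum sizes and rates, two-sided 0.05, and both arms reaching full size.

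A reader might infer more than the documents support:

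- That the test is invalid or raises the false-positive risk. It is valid; ignoring a prognostic stratification factor pushes the size down. With equal rates the pooled test's 0.054 is a small-sample feature unrelated to stratification.
- That the primary conclusion or the choice of arm is affected. Neither uses this test.
- That an unstratified test is also planned for ORR and safety. No test is named for either.
- That disease type was chosen because response was expected to depend on it. This is plausible, but no section says so.

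**What to change.** In section 14.0, replace the two-sample proportion test for systemic response with an asymptotic Cochran-Mantel-Haenszel test, without continuity correction, stratified by disease type as randomised. Report a stratified risk difference with a 95% CI, and state the significance level and sidedness. Name the same method for ORR, where a test is missing. Keep the exact conditional version at most as a sensitivity analysis.

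List the levels of disease type and say how sparse strata will be handled. A stratum with patients in only one arm, or with no responders, adds nothing to the test. The change is not extended to adverse events, because the documents give no reason to expect toxicity to vary by disease type.

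The cost is wording only. The per-arm Simon rules, the maximum of 30 evaluable patients, the expected enrolment of up to 34 and the selection table stay as they are. The statistical price is up to about 1 point of power if tumour types respond alike. Even the stratified test keeps low power for realistic differences (about 0.12 to 0.16 at an odds ratio of 2.2), so the plan's caution about this comparison should remain.
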